### 9.3.2.1 Thrombosis With Thrombocytopenia Syndrome

As previously noted, case definitions will be specified in the SAP, however, given its clinical importance, additional details for defining TTS are provided here. As of May 2021, no TTS standard case definition has been accepted for use by all countries ([Brighton Collaboration 2021b](#)). The Brighton Collaboration interim case definition for TTS (version 10.16.2, 18 May 2021) defines TTS as “Any patient presenting with both acute venous or arterial thrombosis AND new-onset thrombocytopenia (TCP)” [as confirmed by both the Brighton Case Definitions for thrombocytopenia and thrombosis ([Brighton Collaboration 2021a](#), [Wise et al 2007](#))]. The Brighton Collaboration case definition for TCP ([Wise et al 2007](#)) requires evidence of a platelet count of less than  $150,000/\mu\text{L}^3$ .

[figure not shown]
Because laboratory measurements of platelet counts are not expected to be available for most proposed data sources, the case definition of TTS for the current study has been adapted to qualify TCP based on a diagnosis code. In addition, diagnoses that qualify for thrombosis do not include acute myocardial infarction (AMI) or stroke, which is consistent with the May 2021 Centers for Disease Control and Prevention (CDC) working case definition for TTS following COVID-19 vaccination ([CDC 2021](#)). It should be emphasised that the proposed case definition for this study is provisional and subject to change as the Brighton case definition evolves and in response to findings from validation exercises. Because the concept of “thrombosis” also includes embolic events, for purposes of the case definition, the concept has been relabeled “thromboembolic event” (TE).

The working TTS case definition for this study requires:

- A new qualifying TE (defined below) AND
- A new diagnosis of TCP (or laboratory evidence of the same, where available) that is made from 10 days before and up to 10 days after that event (<https://zenodo.org/record/5255870#.Yx8KBHZBxPZ>) ([Burn et al 2022](#))

[Figure 5](#) shows the look-back (“washout”) periods proposed to define “new” diagnoses.

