#### **9.3.2.1.1 EXPERT REVIEW OF TTS CASES IDENTIFIED IN AUTOMATED DATA**

Review of clinical records in hospital charts for potential cases of TTS by research team clinicians will be requested as per access and approval by hospitals in PHARMO, VID, and ARS Toscana. In SIDIAP, additional review can be requested from the general practitioners

(GPs), who have access to the discharge letters. In CPRD, and for any potential cases of TTS in other data sources where hospitals do not grant access for record review, patient profile review will be performed. The electronic patient profile is a cumulative chronologically ordered record of all available electronic linkable information. This record will be reviewed by members of each local research team who are blinded to vaccination status, wherever possible.

It is anticipated that reviewers will be physicians and other life science professionals who will apply a standardised case definition of TTS (to be finalised). Data sought will include platelet counts, evidence documenting the thrombus and location, evidence of recent heparin exposure, and any evidence that a specific alternative diagnosis to TTS (eg, thrombotic thrombocytopenic purpura) accounted for the clinical presentation.

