### 9.7.7 Crude and Adjusted Measures of Association: Cohort Design

The analyses described below will address primary objective 4 and exploratory objectives 2.

- The analysis will compare subjects vaccinated with AZD1222 with the concurrent unvaccinated comparators and historical comparators to estimate the effect of receiving any dose (a first or a second), under the assumption that the effect of either dose is homogeneous. The effect of each individual dose on AESIs, will be estimated as prior vaccine exposure may “prime” the immune system.
- For outcomes that have **known risk windows**, we propose to estimate crude and adjusted IRRs and IR differences with 95% CIs using Poisson regression models. Specifically, the IRRs would be estimated using Poisson regression with robust estimation of the variance to account for individuals who may contribute person-time at different points to the exposed and unexposed cohorts (Zou 2004). For anaphylaxis and sudden death, crude and adjusted PPRs and PPDs with 95% CIs will be estimated using Poisson regression models with robust estimation of the variance to account for individuals who may contribute person-time to the exposed and unexposed cohorts at different timepoints.
- For outcomes **with unknown risk windows**, we propose estimating crude and adjusted relative risks and absolute risk differences. The relative risk (HRs) and 95% CI will be estimated using Cox regression models with robust estimation of the variance time-to-event analyses (Allison 2010). Using Cox regression models allows the flexibility to potentially adjust for time-dependant covariates, such as intercurrent COVID-19 infection.
- Adjustment for confounding will occur using PS, either through PS matching or by analytic methods involving stratification or weighting, which will be specified in the SAP. In the event that important covariates remain imbalanced after final selection of the cohorts for comparative analyses, additional approaches for confounding adjustment will be considered, including double-robust methods (ie, including the covariate in the outcome model as a separate term) or through analyses that restrict the population to subjects with more similar baseline characteristics (eg, subjects without substantial comorbidity).

The analysis described below will address exploratory objective 3

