### 9.7.10 Sensitivity Analyses

For each of the matched cohort populations (ie, AZD1222 cohort with concurrent unvaccinated comparator cohort, AZD1222 cohort with active comparator cohort, and AZD1222 cohort with historical comparator cohort), the following sensitivity analyses will be conducted analogously to the main analysis:

- The direct effect of vaccination with AZD1222 on the AESIs will be estimated, excluding subjects with prior COVID-19 diagnosis and thus censoring their follow-up at the occurrence of a COVID-19 diagnosis.
- The effect of partial censoring within matched pairs on the AESIs will be estimated by censoring both members of a matched pair when one member is censored.
- For thrombocytopaenia with bleeding, an alternative risk window of 1 to 28 days at the index date (instead of the 1 to 42 days in the primary analysis) will be assessed.
- For TTS; 3 alternative risk windows of 1 to 14 days, 1 to 21 days, and 1 to 28 days after the index date (instead of 1 to 42 days in the primary analysis) will be assessed.
- For TTS; an alternative definition of the outcome will include not only thrombocytopaenia with venous thromboembolisms but also thrombocytopaenia with AMI or stroke. The risk window between thrombocytopaenia and AMI or stroke will be the same as the one used for venous thromboembolism, ie, 10 days.
- For TTS; AESI cases will be restricted to confirmed cases (ie, excluding cases that could not be validated). The resulting positive predictive values (PPVs) will be used to correct the observed PPV from the main results. This analysis will be performed depending on the total number of outcomes that will be validated (as detailed in Section 9.3.2.1.1).
- In CPRD, a sensitivity analysis using hospital data to assess the AESIs will be performed at the time of the final analysis. However, depending on the duration of the lag time for hospital data at the time of the final analysis, the analysis using hospital data may be considered as the primary analysis.

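### TTS validation analysis (Protocol 9.7.10): the PPV correction is aimed at a quantity the main results do not contain, and cases that review could not settle are not separated from refuted ones

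*Protocol*

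**What the plan says.** The TTS bullet in Protocol 9.7.10 has three parts.

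- Case set: "AESI cases will be restricted to confirmed cases (ie, excluding cases that could not be validated").
- Correction: the PPVs that result "will be used to correct the observed PPV from the main results".
- Status: "This analysis will be performed depending on the total number of outcomes that will be validated".

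Four other places bear on it.

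- **What the main analysis yields.** TTS has a primary risk window of 1 to 42 days (Table 3), so it counts as an AESI with a known risk window. Section 9.7.6 gives incidence rates for these. Section 9.7.7 adds the comparison: "we propose to estimate crude and adjusted IRRs and IR differences with 95% CIs using Poisson regression models".
- **How cases are reviewed (9.3.2.1.1).** Hospital chart review "will be requested as per access and approval by hospitals in PHARMO, VID, and" ARS Toscana. In SIDIAP, general practitioners who hold discharge letters can be asked. In CPRD, and for cases elsewhere "where hospitals do not grant access for record review, patient profile review will be performed". The local reviewers of these profiles are people "who are blinded to vaccination status, wherever possible".
- **What the reviewers look for.** Platelet counts and evidence of the thrombus are among the data sought (9.3.2.1.1). Yet 9.3.2.1 says that "laboratory measurements of platelet counts are not expected to be available for most proposed data sources".
- **Which measure matters.** Section 9.5 prefers absolute to relative measures for judging the public health impact of TTS, and sizes TTS on the absolute risk difference (Table 7).

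**The concern.** There are two separate faults in one bullet.

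First, the correction has the wrong target. A PPV comes out of case review and can be used to scale an observed count, rate or rate difference. The main analysis produces no PPV, so there is none to correct. An analyst would have to guess which estimate is meant and which cases belong in the PPV denominator.

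Second, the exclusion rule does not distinguish a case that was reviewed and refuted from one that review could not settle. The second kind is foreseeable, because a profile may lack the platelet count the reviewer needs. Dropping such a case treats it as a non-case, so any true case among them is lost from the numerator while the person-time stays in the denominator.

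At stake is the absolute TTS risk among confirmed cases. It would err in the reassuring direction, for a safety concern that the protocol says is best judged on the absolute scale.

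**Working it through.** **Step 1: the plan's own figure.** For a 4-week TTS risk of 1 per 100,000, background zero and N = 1,000,000, Table 7 gives probabilities 0.35, 0.89, >0.99 and >0.99 that the upper 95% limit of the risk difference lies below 1.5, 2.0, 2.5 and 3.0 per 100,000.

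Formula: P = Φ((threshold − RD)/SE − 1.96), with SE = √(p(1 − p)/N) = √(0.00001 × 0.99999 / 1,000,000), or 0.316 per 100,000.

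Results: 0.352, 0.885, 0.997, 1.000. All 40 cells of Table 7 reproduce within 2 points. The planning risk, equal to 10 true cases per million vaccinated, is therefore a sound base for the illustration.

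**Step 2: the correction target.** Sections 9.7.6 and 9.7.7 list the main outputs for TTS: rates, rate ratios and rate differences. None is a PPV. This step needs no assumption.

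**Step 3: effect of the exclusion.** Let F be the flagged cases, v the share that review can settle and p the PPV. The protocol gives neither v nor p. Assumptions: v from 0.5 to 1.0, p = 0.8 or 0.5, and v independent of true status.

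- True cases: F·p = 10, so F = 12.5 at p = 0.8 and 20 at p = 0.5.
- Confirmed-only count: F·v·p = 10v.
- All flagged cases scaled by confirmed / (confirmed + refuted): F·p = 10.
- All flagged cases scaled by confirmed / all flagged: F·v·p = 10v.
- Uncorrected main analysis: F.

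| v | Confirmed only, per 100,000 | PPV among assessable cases | PPV among all flagged cases |
|---|---|---|---|
| 1.0 | 1.0 | 1.0 | 1.0 |
| 0.9 | 0.9 | 1.0 | 0.9 |
| 0.8 | 0.8 | 1.0 | 0.8 |
| 0.7 | 0.7 | 1.0 | 0.7 |
| 0.6 | 0.6 | 1.0 | 0.6 |
| 0.5 | 0.5 | 1.0 | 0.5 |

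The shortfall is 1 − v whatever the PPV, and is zero at v = 1. The uncorrected main rate is 1.25 per 100,000 at p = 0.8 and 2.0 at p = 0.5, so it errs upward. The choice of PPV denominator decides whether the correction removes the shortfall or repeats it.

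**Step 4: if assessability depends on true status.** Take 100 flagged cases, v = 0.7 and PPV 0.8 among the 70 assessable. Confirmed: 70 × 0.8 = 56. PPV-scaled: 100 × 0.8 = 80.

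| PPV in the 30 non-assessable | True cases | Confirmed only / true | PPV-scaled / true |
|---|---|---|---|
| 0.2 | 56 + 6 = 62 | 0.90 | 1.29 |
| 0.5 | 56 + 15 = 71 | 0.79 | 1.13 |
| 0.8 | 56 + 24 = 80 | 0.70 | 1.00 |
| 1.0 | 56 + 30 = 86 | 0.65 | 0.93 |

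PPV scaling is exact only when the non-assessable cases have the same PPV. Counting them as all false or all true gives 56 to 86, which contains the truth in every row if the review verdicts are correct.

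**Step 5: the rate ratio.** With the same v in both cohorts it cancels. If v differs, the confirmed-only ratio is multiplied by v₁/v₀: 0.8/0.6 = 1.33, or 0.6/0.8 = 0.75. This is why the review results should be shown by cohort where numbers allow.

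**The case against.** The strongest reply is that nothing here lowers a primary estimate. This is a sensitivity analysis, run only if enough cases are validated. The main TTS analysis keeps every case the algorithm flags, and is too high rather than too low if the PPV is below 1. That stands.

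The reply continues that the PPV step, read sensibly as the main rate times the PPV among assessable cases, removes the shortfall rather than causing it. That also stands as a reading. But the text names neither the estimate to be scaled nor the denominator, and the other denominator repeats the shortfall.

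A reader might infer that a large share of cases will go unreviewed, because chart access depends on hospitals and CPRD, which relies on profile review, holds 3,938,490 of 5,557,094 matched vaccinees (70.9%, Table 4). The documents do not support this. Section 9.3.2.1.1 gives a profile or general practitioner review where charts are not used, so every flagged case is meant to get some review. Section 9.4.1 describes laboratory results, discharge summaries and validation against original letters in CPRD. The 70.9% is a share of vaccinees and says nothing about how many TTS cases are inconclusive. What remains is narrower: some reviews may not settle the case.

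Finally, the validation details could be left to the SAP, and 9.9.1 allows for bias analyses of misclassification. That is fair for the finer detail. It does not cover a correction rule stated here with a target that does not exist, or an exclusion stated here that can merge two kinds of case.

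**Conclusion.** The point holds in a limited form. The correction as written cannot be carried out, and that conclusion needs no assumption. The exclusion makes the confirmed-only absolute TTS risk too low whenever true cases are among those that review could not settle. If assessability is independent of true status, the shortfall equals the non-assessable share.

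A reader might go further and say that the analysis would understate the TTS risk, or attach a percentage. The documents do not support either. They give no non-assessable share and no PPV, and the share may be near zero given the fallback review. If the exclusion is meant to cover only cases reviewed and refuted, there is no shortfall at all. The values of v above show how the error behaves; they are not an estimate of it. The main TTS estimate is not affected.

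**What to change.** In the TTS bullet of 9.7.10:

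1. Classify each flagged case as confirmed, refuted or not assessable, and report all three counts by data source and cohort.
2. Define PPV = confirmed / (confirmed + refuted), by data source and, where numbers allow, by cohort.
3. Replace the reference to correcting an observed PPV with: *correct the observed TTS counts, incidence rates and rate differences*.
4. Report bounds with non-assessable cases counted as all true and as all false. PPV scaling assumes a similar PPV in those cases, and step 4 of the working shows that it can miss in either direction.

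The cost is a few sentences, one extra review category and a simple reweighting. No additional case review is needed and the main analysis does not change.

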#### 9.7.10.1 Negative Control Outcome

For the matched cohorts, cumulative incidence (1 – KM estimate) and curves of urinary tract infections and non-pathological fractures within 12 days after the index date will be produced using the inverse probability of treatment weighting from the main analysis. The KM estimator will be estimated as for the main analysis (Section 9.7.6).

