**Table 1 Amendments, Updates, and Adjustments**

Version number	Date	Section of study protocol	Amendment or update	Reason
4.0	10 Oct 2022	9.3.2 Table 2	Split AESI group categories when events in the category have different risk windows, ie, split stress myocardiopathy from “acute cardiac injury” and transverse myelitis from “multiple sclerosis and other demyelinating disorders” (applied in analyses for Interim Report 2)	Alignment with the analysis conducted for Interim Reports 1 and 2. To avoid analysing together the components within a composite AESI that have different risk windows
4.0	10 Oct 2022	9.7.7	For 2 AESIs with known risk windows (anaphylaxis and sudden death) prevalence proportion, prevalence proportion rate, and prevalence proportion difference will be estimated instead of IR, IRR, and IRD (applied in analyses for Interim Report 2)	Based on PRAC-endorsed SAP (V1.0, 10 Nov 2021). For anaphylaxis and sudden death, due to extremely short risk windows, the time to the event is not considered relevant in the analysis
4.0	10 Oct 2022	9.7.10	New sensitivity analysis: inclusion of a sensitivity analysis where TTS also includes AMI or stroke (applied in analyses for Interim Report 2)	To assess the potential effect of AZD1222 on arterial thrombosis and thromboembolisms
4.0	10 Oct 2022	9.7.10.1	New sensitivity analysis: negative control outcome analysis. The 2 negative control outcomes selected are fractures and urinary tract infections (applied in analyses for Interim Report 2)	Based on PRAC recommendation in the AR for the SAP (10 Jun 2022); to evaluate the presence of residual confounding
4.0	10 Oct 2022	9.7.3.4	Feasibility assessment of cohort comparability for the active comparator population (to be applied in the Feasibility Assessment Report)	To assess the comparability between the AZD1222 and the active comparator cohorts

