**Figure 4. Time at Risk for an AESI With a Known Risk Window in Subjects With 2 Doses of AZD1222**

AESI, adverse event of special interest.

- For the evaluation of AESIs with an **unknown risk window** (those with a risk window that ends at 180 or 365 days), follow-up will comprise all person-time after the index date and will extend 180 or 365 days (Table 3) after the last AZD1222 or mRNA vaccine dose (dose 1 if only 1 dose was received and dose 2 if 2 or more doses were received) for vaccinated subjects or the corresponding time for the unvaccinated and historical comparators.
- For the AZD1222 cohort:
  - 365 days after the second vaccine dose. This rationale is 2-fold. First, because we expect that most comparators will become vaccinated during the study period, this choice will reduce the anticipated mismatch of follow-up time duration between the exposed and comparator cohorts. Second, although the risk window for some AESIs is not defined, vaccine-associated adverse events are unlikely to manifest beyond 1 year. To include person-time in the risk window when a vaccine effect could not reasonably occur may attenuate risk estimates, if a true risk exists.
  - The date on which the subject received a dose of any COVID-19 vaccine other than AZD1222.
  - The date on which a subject receives a 3rd dose of any COVID-19 vaccine
- For the active comparator cohort:
  - 365 days after the second vaccine dose.
  - The date on which the subject received a dose of any COVID-19 vaccine other than Comirnaty or Spikevax.
  - The date on which a subject receives a 3rd dose of any COVID-19 vaccine
- For the concurrent unvaccinated cohort, the date on which the subject received a dose of AZD1222, at which time the subject switches from the comparator to the AZD1222 cohort.

- For the historical comparator cohort, 31 October 2019, an estimate of the date when SARS-CoV-2 started to circulate in Europe.

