**Table 3 Adverse Events of Special Interest and Other Safety Concerns**

Adverse event	Suitable for SCRI analysis according to ACCESS protocol template a	Risk interval after index date (days)	Clean look-back interval (days) k
Vaccine-associated enhanced disease, including vaccine-associated enhanced respiratory disease, including ARDS	No	14-365 b	365
Multisystem inflammatory syndrome in adults/children	Yes	1-42 c	365 c
Sudden death	No	0-6 b	Not applicable
Autoimmune thyroiditis	No d	1-180 e	365
Anosmia, ageusia	No f	1-365 e	365
Anaphylaxis	Yes	0-2 c	180 c

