**Table 3 Adverse Events of Special Interest and Other Safety Concerns**

Adverse event	Suitable for SCRI analysis according to ACCESS protocol template a	Risk interval after index date (days)	Clean look-back interval (days) k
Type III hypersensitivity reactions	No d	1-365 e	365
ARDS	Yes	1-28 j	365
Guillain-Barré syndrome	Yes	1-42 c	365 c
Other peripheral and polyneuropathies	No d	1-42 c	365 c
Multiple sclerosis, and other demyelinating disorders	No d	1-365 e	365 c
Transverse myelitis	Yes	1-90 c	365 c
Optic neuritis/neuromyelitis optica spectrum disorder	Yes	1-42 c	365 c
Encephalitis (including acute disseminated encephalomyelitis)	Yes	1-42 b	183 c
Myasthenia gravis	No d	1-365 e	365
Bell's palsy	Yes	1-42 c	365 c
Generalised convulsions	Yes	0-14 c	365
Narcolepsy	No	1-42 c	365 c
Myocarditis/pericarditis	Yes	1-42 c	365 c
Postural orthostatic tachycardia syndrome	No d	1-42 b	365 c
Myocardial infarction	Yes	1-28 c	365 c
Acute cardiac injury including microangiopathy, cardiogenic shock, and heart failure	No f	1-90 e	365
Stress cardiomyopathy	No f	1-42	365
Thrombocytopenia	Yes	1-42 b	365 c
Thrombocytopenia with associated bleeding	No d	1-42 g	365 c
Thrombosis (embolic and thrombotic events) without thrombocytopenia	Yes	1-42 c	365 c
Thrombosis with thrombocytopenia syndrome	No d	1-42 g	365
Capillary leak syndrome	No d	1-365 e	365
Acute kidney injury	Yes	1-14 b	365
Acute liver injury	Yes	1-14 b	365
Acute pancreatitis	No d	1-365 e	365

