**Figure 5 Time Windows to Define Thrombosis With Thrombocytopenia Syndrome**

dx, diagnosis.

Thromboembolic events will include new diagnoses of embolism or deep vein thrombosis (DVT) (including splanchnic, intracranial, limb locations) or thromboembolism. According to the working case definition, infarctions (including myocardial and cerebral) and stroke will not qualify as a TE in the main analysis but will be included in a sensitivity analysis in order to evaluate the potential effect of AZD1222 on arterial thrombosis and thromboembolisms. In addition to evaluating TEs overall, it is proposed to evaluate DVT outcomes separately by location of the event into central venous sinus thrombosis, limb thrombosis, and splanchnic area thrombosis. In the primary analysis, the risk window for TTS extends from 1 to 42 days after vaccination (or the corresponding index date for the unexposed comparator subject).

Sensitivity analyses will be conducted:

- Including the TTS definition described previously but adding infarctions (including myocardial and cerebral) and stroke (Interim Report 2 and final study report)
- Using alternative risk windows of 1 to 14 days, 1 to 21 days, and 1 to 28 days after the index date (final study report)

Both TE and TCP will be ascertained using codes for diagnoses, procedures, and treatments in electronic data that are also under development within the studies conducted under the VAC4EU framework.

Identification of the clinical concerns “Thromboses without thrombocytopenia” and “Thrombocytopenia without thrombosis” will follow a similar logic.

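### The negative control outcomes stop at day 12 without a stated reason, so they cannot show bias arising later or, in two of the three comparisons, after dose 2

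*Protocol*

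**What the plan says.** Section 9.7.10.1 defines the analysis for the matched cohorts: results for "urinary tract infections and non-pathological fractures within 12 days after the index date will be produced". It promises "cumulative incidence (1 – KM estimate) and curves of urinary tract infections and non-pathological fractures", with the horizon and weighting fixed as "within 12 days after the index date will be produced using the inverse probability of treatment weighting from the main analysis". The Kaplan-Meier estimation is to follow Section 9.7.6. Table 1 attributes the analysis to a PRAC recommendation and gives its aim as "to evaluate the presence of residual confounding".

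The AESI analyses that this check supports run much longer:

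- Most known-window events in Table 3, for example "Thrombosis (embolic and thrombotic events) without thrombocytopenia", use days 1-42. Section 9.3.2.1 says of thrombosis with thrombocytopenia syndrome (TTS): "In the primary analysis, the risk window for TTS extends from 1 to 42 days after vaccination".
- Sections 9.2.3.1, 9.7.6 and 9.7.7 pool a second window after dose 2. For unvaccinated and historical comparators that window mirrors the timing in the matched vaccinee.
- For unknown-window events, Section 9.2.3.1 says that "follow-up will comprise all person-time after the index date and will extend 180 or 365 days" after the last dose.

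**The concern.** A negative control outcome informs on bias only over the follow-up in which it is measured. Fractures and urinary tract infections are used because the vaccine is not expected to cause them, so a difference between cohorts points to bias. If the look ends at day 12, agreement between the cohorts says little about days 13 to 42, nothing about a dose-2 window starting weeks later, and almost nothing about days 180 to 365.

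The long-window estimates are where reassurance is most needed. Sections 9.1.1 and 9.9.1 say that unvaccinated follow-up was too short for long-window events and that the historical and active comparators were added for this reason. The same sections concede doubts about the comparability of both. Section 9.7 commits the study to interpreting magnitude, precision and possible bias, but a curve to day 12 gives no bias estimate on the scale of the incidence rate ratio or hazard ratio reported for the AESIs.

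**Working it through.** **1. Count of windows (Table 3, 37 rows), by last day of the risk interval.**

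| Ends on day | 2 | 6 | 14 | 28 | 42 | 90 | 180 | 365 |
|---|---|---|---|---|---|---|---|---|
| Rows | 1 | 1 | 3 | 2 | 16 | 2 | 1 | 11 |

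Only anaphylaxis (0-2) and sudden death (0-6) end by day 12, so 37 - 2 = 35 rows (95%) end on day 14 or later. Three of the 35 start after day 12: vaccine-associated enhanced disease (14-365), fibromyalgia (91-365) and chronic fatigue syndrome (183-365). The other 32 start on day 0 or 1 and include the first 12 days.

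**2. Share of the window seen by day 12.** 12/14 = 86%; 12/28 = 43%; 12/42 = 29%; 12/90 = 13%; 12/180 = 7%; 12/365 = 3%. Against the 84 days over two doses assumed in Tables 5 and 6, 12/84 = 14%.

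**3. Dose 2.** Section 7 places dose 2 at 28 to 84 days after dose 1. With the index date at dose 1 (unvaccinated and historical comparisons), day 12 falls before any dose 2 on that schedule. In the active comparison the index date is the second dose (Section 9.2.1.1.3), so there the 12 days do lie in the dose-2 window.

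**4. What a 12-day look can detect.** The protocol gives no precision figure for the negative controls, so I first checked the method on its own tables. With true ratio 1, P(upper limit < x) = Φ(ln x / SE - 1.96), where SE = √(1/E1 + 1/E0). For Guillain-Barré syndrome in Table 6, E = 5,000,000 × 84/365.25 × 2/100,000 = 23.0 per cohort, SE = 0.295, and for x = 3 the result is 0.961 against the stated 0.96. With 3:1 person-time (Table 5) it is 0.750 against 0.75.

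Applied to the negative controls, power to detect a constant bias ratio b is Φ(|ln b| / SE - 1.96). The matched counts in Table 4 sum to 3,938,490 + 517,015 + 609,842 + 336,889 + 154,858 = 5,557,094. The background rate is not in the protocol; I assume 300 to 3,000 per 100,000 person-years. At 300, E0 = 5,557,094 × 12/365.25 × 300/100,000 = 548.

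| Population | Rate per 100,000 PY | b = 0.8 | b = 0.9 | b = 1.1 | b = 1.2 |
|---|---|---|---|---|---|
| All sources | 300 | 0.94 | 0.40 | 0.36 | 0.88 |
| All sources | 1,000 | 1.00 | 0.87 | 0.84 | 1.00 |
| PHARMO only | 300 | 0.08 | 0.05 | 0.05 | 0.08 |
| PHARMO only | 3,000 | 0.45 | 0.14 | 0.13 | 0.38 |

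These powers assume 1:1 person-time and independent subjects, so they are optimistic. The all-source rows also presuppose pooling.

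**5. What it cannot detect (illustration with assumed values).** Let the bias ratio be 1.0 to day 12 and 1.3 afterwards. The check reads 1.00. The average over days 1-42 is (12 × 1.0 + 30 × 1.3)/42 = 1.21, and over 365 days it is (12 × 1.0 + 353 × 1.3)/365 = 1.29.

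**6. Loss of unvaccinated comparators.** Section 9.1.1 reports a median follow-up under 2 months. If censoring is exponential with a 60-day median (assumed), the share censored by day d is 1 - 2^(-d/60): 13% by day 12, 38% by day 42 and 87.5% by day 180. With a 30-day median the shares are 24%, 62% and 98%.

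**The case against.** A reader might infer that the negative controls cannot detect residual confounding at all. The documents do not support that. The confounding described in Section 9.9.1 (healthy vaccinee bias, confounding by indication, unmeasured lifestyle) is largely present at baseline and can show from the first day. So can changes in background rates and care-seeking between 2017-2018 and the pandemic. Step 4 shows that a moderate constant bias would probably be seen in pooled data, though not in the smallest source alone.

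Three other tempting readings also fail:

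- **That only curves are produced.** The text promises cumulative incidence as well, from which a difference follows. What is absent is a named contrast with a confidence interval, and the statistical analysis plan, not available here, may supply it.
- **That the check fails at detecting differential censoring.** That is not its stated purpose. Section 9.7.10 has a separate pair-censoring analysis, and Section 9.7.1 describes follow-up by cohort.
- **That no dose-2 window is covered in any comparison.** The active comparison is indexed at dose 2.

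There is also a possible rationale for a short horizon. Table 1 separates direct vaccine effects from indirect effects through prevented infection. Over long follow-up, prevented COVID-19 could alter care contact and hence recorded fractures or urinary infections, making a late control less clean. This is inference, since the protocol does not offer it as the reason. It supports cautious reading of late results, and does not justify leaving days 13 to 42 and the dose-2 windows untested.

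**Conclusion.** The concern holds in this limited form. The 12-day horizon is fixed in the protocol, is unexplained, and is shorter than 35 of 37 AESI windows. The check is informative about bias acting from day 0. It is blind to bias arising after day 12 and, in the unvaccinated and historical comparisons, to bias in the dose-2 windows. The counts and coverage shares come directly from Table 3 and the dose-2 conclusion from the labelled schedule; none of these needs an outside assumption. The power figures depend on the assumed event rates, the later-bias example on a chosen ratio of 1.3, and the censoring shares on an exponential form.

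A reader might also infer that 12 days is a slip for a longer period. The document cannot settle that, so the sponsor should confirm the figure.

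**What to change.** Confirm the 12-day figure and state the reason for it. Keep the 12-day curves and add the following to Section 9.7.10.1, for both negative control outcomes and each comparator, with the same matching, weights and censoring as the main analysis:

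- **Known windows:** the Poisson rate ratio and rate difference over days 1-42 after each dose in the unvaccinated and historical comparisons, and after dose 2 in the active comparison.
- **Unknown windows:** the Cox hazard ratio and the difference in cumulative incidence to days 180 and 365 for comparators with adequate follow-up. The unvaccinated comparison should be read cautiously beyond its median follow-up of under 2 months.
- **Reporting:** each weighted ratio and difference with a 95% CI, shown by data source beside the corresponding AESI estimates.

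The cost is a few extra model runs and possibly longer ascertainment of two outcomes already being extracted. The real downside is interpretive: late estimates may partly reflect prevented COVID-19 and unequal censoring. They should therefore be read together with the pair-censoring and COVID-19-censoring sensitivity analyses already planned in Section 9.7.10.
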